4. STUDY POPULATION

4.1. Inclusion Criteria

Subjects must satisfy all of the following criteria to be eligible for the study:

1. Children with cardiac diseases who are at risk for thromboembolic complications and require at least 3 months antithrombotic anticoagulant prophylaxis.

Either one of the following criteria may apply:

a. Children with cardiac disease who have a history of cardiac shunt occlusion/thrombosis, with shunt still in place (secondary prevention).

OR

b. Children with cardiac disease who require (including those already taking, and those not yet taking) anticoagulation for primary prevention of TE.

Cardiac conditions known to significantly increase the risk of thrombosis (hence, indications for primary TE prevention) are defined in Antithrombotic Therapy and Prevention of Thrombosis¹. Some examples of cardiac conditions at risk of thrombosis are Fontan surgery, heart failure, Kawasaki disease, and Blalock-Taussig and Glenn surgery.

- 2. Male or female children between 1 and <18 years of age. Children between 38 weeks gestational age and 1 year of age will be included in the study, however, only after the safety and efficacy data of 50 subjects between 1 and <18 years of age in the edoxaban arm have been evaluated at the end of the 3-month treatment period.
- 3. Subject and/or parent(s)/legal guardian(s) or legally acceptable representative is informed and provides signed consent for the child to participate in the study with edoxaban treatment. Pediatric subjects with appropriate intellectual maturity will be required to sign an assent form in addition to the signed informed consent from the parent(s)/legal guardian(s) or any legally acceptable representative.
- 4. Female subjects of childbearing potential must test negative for pregnancy at Randomization and must consent to avoid becoming pregnant by using a locally approved contraception method throughout the study. For locally approved contraceptive methods, see Appendix 17.3.
- 5. If the subject has a history of a TE that meets all of the following criteria:
 - Old, organized and/or resolved per the discretion of the Principal Investigator (confirmation of an old, organized and or resolved TE is not required by any imaging studies), and
 - The subject is asymptomatic, and
 - The subject continues to require at least 3 months of anti-coagulation treatment, and
 - There is no intracardiac thrombus or thrombi on the screening echo, and
 - All other inclusion and exclusion criteria are met.

4.2. Exclusion Criteria

Subjects who meet any of the following criteria will be disqualified from entering the study:

- 1. Subjects with a history of the following up to randomization:
 - Symptomatic venous or arterial TE
 - Asymptomatic venous or arterial TE found by routine imaging
 - Asymptomatic intracardiac thrombosis confirmed by an echocardiogram during study screening period.

Note: Valid echocardiograms are defined here as images taken within 5 weeks prior to Randomization Visit.

- 2. Subjects with mechanical heart valves.
- 3. Subjects with active bleeding or high risk of bleeding contraindicating treatment with anticoagulant.
- 4. Subjects with a contraindication to the use of heparin (UFH or LMWH) and/or VKA (see Appendix 17.4).
- 5. Co-administration of antithrombotic therapy is contraindicated in edoxaban arm and SOC arm except for low dose aspirin defined as 1 to 5 mg/kg/day with maximum of 100 mg/day (see Appendix 17.5).
- 6. Administration of rifampin is prohibited during the study and subjects on concomitant use of rifampin are excluded (see Appendix 17.5.6).
- 7. a) Subjects with severe hepatic impairment or hepatic disease associated with coagulopathy (eg, acute hepatitis, chronic active hepatitis, and cirrhosis).

b) Subjects with ALT >5 × the upper limit of normal (ULN) or total bilirubin (TBL) >2 × ULN with direct bilirubin >20% of the total at Screening.

c) Subjects with aPTT >50 seconds or international normalized ratio [INR] >2.0 not related to anticoagulation therapy at Screening.

- 8. Subjects with estimated glomerular filtration rate (eGFR) <30% of normal for age and size (see Appendix 17.9).
- 9. Subjects with stage 2 hypertension defined as blood pressure (BP) systolic and/or diastolic confirmed >99th percentile plus 5 mmHg (see Appendix 17.10).
- 10. Subjects with thrombocytopenia (thrombocytes $<50 \times 10^9/L$).
- 11. Subjects with Fontan procedure with a history of or signs/symptoms suggestive of protein-losing enteropathy.
- 12. Subjects with a life expectancy less than the expected study duration (3 months).
- 13. Subjects who are known to be pregnant or breastfeeding.

- 14. Subjects who are not using an approved method of contraception (see Appendix 17.3).
- 15. Subjects with any condition that, as judged by the Investigator, would place the subject at increased risk of harm if he/she participated in the study including contraindicated medications identified in Appendix 17.6.
- 16. Subject who participated in another interventional clinical study or treated with an experimental therapy with less than a 30-day wash-out period prior to the Screening Visit.
- 17. If any imaging is performed prior to randomization and results show a newly detected unorganized thrombus, these subjects are NOT eligible for the study.
- 18. Hypersensitivity to the active ingredient or to any of the excipients of any components of the trial treatment.
- 19. Patients with a history of thrombosis who are diagnosed with antiphospholipid syndrome who are triple positive (for lupus anticoagulant, anticardiolipin antibodies, and anti-beta 2-glycoprotein I antibodies.

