 - Old, organized and/or resolved per the discretion of the Principal Investigator (confirmation of an old, organized and or resolved TE is not required by any imaging studies), and
 - The subject is asymptomatic, and
 - The subject continues to require at least 3 months of anti-coagulation treatment, and
 - There is no intracardiac thrombus or thrombi on the screening echo, and
 - All other inclusion and exclusion criteria are met.

Exclusion Criteria

Subjects who meet any of the following criteria will be disqualified from entering the study:

- 1. Subjects with a history of the following up to randomization:
 - Symptomatic venous or arterial TE
 - Asymptomatic venous or arterial TE found by routine imaging
 - Asymptomatic intracardiac thrombosis confirmed by an echocardiogram during the study screening period.

Note: Valid echocardiograms are images taken within 5 weeks prior to Randomization Visit.

- 2. Subjects with mechanical heart valves.
- 3. Subjects with active bleeding or high risk of bleeding contraindicating treatment with anticoagulant.
- 4. Subjects with a contraindication to the use of heparin (UFH or LMWH) and/or VKA (see Appendix 17.4).
- 5. Co-administration of antithrombotic therapy is contraindicated in edoxaban arm and SOC arm except for low dose aspirin defined as 1 to 5 mg/kg/day with maximum of 100 mg/day (see Appendix 17.5).

- 6. Administration of rifampin is prohibited during the study and subjects on concomitant use of rifampin are excluded Appendix 17.5.6.
- 7. a) Subjects with severe hepatic impairment or hepatic disease associated with coagulopathy (eg, acute hepatitis, chronic active hepatitis, and cirrhosis).

b) Subjects with ALT >5 × the upper limit of normal (ULN) or total bilirubin >2 × ULN with direct bilirubin >20% of the total at Screening.

c) Subjects with aPTT >50 seconds or international normalized ratio [INR] >2.0 not related to anticoagulation therapy at Screening.

- 8. Subjects with estimated glomerular filtration rate (eGFR) <30% of normal for age and size (see Appendix 17.9)
- Subjects with stage 2 hypertension defined as blood pressure systolic and/or diastolic confirmed >99th percentile plus 5 mmHg (see Appendix 17.10).
- 10. Subjects with thrombocytopenia (thrombocytes $<50 \times 10^{9}$ /L).
- 11. Subjects with Fontan procedure with a history of or signs/symptoms suggestive of protein-losing enteropathy.
- 12. Subjects with a life expectancy less than the expected study duration (3 months).

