5.6.3. Reasons for Discontinuation from Study Treatment

Subjects may **discontinue the treatment** for any of the following reasons:

Proprietary and Confidential Page 66

- 1. End of requirement for anticoagulant therapy
- 2. Reasons related to adverse events (AEs):
 - If initiating or continuing study drug places the subject at undue hazard as determined by the Investigator;
 - If the subject had a serious adverse event (SAE) or other safety concern that is related to study drug treatment as determined by the Investigator;
 - If the subject had a major bleeding event as determined by the Investigator;
 - If the subject has an aggravation or new occurrence of renal insufficiency with estimated eGFR <30% of normal for age and size (Cockcroft-Gault equation for pediatric subjects ≥12 years of age and modified Schwartz equation for pediatric subjects <12 years of age);
 - If the subject demonstrates hepatic test abnormalities including:

Elevation of alanine transaminase (ALT) and/or aspartate transaminase (AST) \geq 3 × ULN and TBL \geq 2 × ULN simultaneously.

ALT and/or AST $\ge 8 \times$ ULN requires an immediate interruption of study drug treatment and prompt repeat testing to confirm abnormality.

- If the subject demonstrates clinical jaundice that requires an immediate interruption of study drug treatment and prompt repeat testing to confirm abnormality;
- If the subject has any elevation of transaminases combined with clinical symptoms of liver injury;
- If a subject discontinues study drug due to confirmed liver enzyme abnormalities or jaundice. The subject will have additional evaluations at the discretion of the Investigator as follows:

Hepatitis A, B, C, and E screening (anti-HAV IgM, HBsAg, anti-HCV plus viral titer, and evaluation for Hep E);

Abdominal ultrasound;

Antinuclear antibody (ANA) and anti-SmAb;

Cytomegalovirus (CMV);

Epstein-Barr virus (EBV);

Additional evaluations as deemed appropriate by the Investigator to exclude other causes of liver enzyme and TBL elevations.

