- An aPTT and INR assessment will be done for all subjects at Screening at local laboratory. Ensure that the subject qualifies with regard to the following central safety laboratory and radiology tests for exclusion criteria:

Echocardiogram. Note: Valid echocardiograms are images taken within 5 weeks prior to Randomization Visit. Note: The presence of a thrombus will disqualify the subject from the study.

Liver function assessments (ALT, AST, TBL, ALP) (central laboratory)

aPTT and INR (assessed locally)

Serum chemistry panel, serum creatinine, and eGFR (central laboratory)

Hematology (central laboratory)

Urinalysis (at central laboratory if dipstick is abnormal)

Note: Urinalysis can be done at local laboratory. Results of urinalysis performed at Screening by local laboratory may be used for qualification

• To expedite qualification and randomization for subjects living a distance from the Investigator site, the site may choose to use their local laboratory for screening eligibility labs. The sample should be split with analysis at both the central laboratory as well as the local laboratory. For the purpose of eligibility, the local laboratory results (aPTT, INR, ALT, TBL, eGFR, and platelet) will be utilized and entered into the eCRF.

If subjects are fulfilling eligibility conditions at the Screening/Qualification Visit, the Investigator has the option to randomize the subject at any time within 30 days. The Screening Visit and Randomization Visit may occur on the same day.

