6.3. Randomization (Day 1, Visit 2)

Investigators will maintain a confidential subject identification code list of names of all subjects randomized to study to allow the Investigator to reveal the identity of any subject when necessary. If all procedures and tests done before randomization confirm the subject's eligibility (Section 6.2) for the study, then the IXRS will be contacted to randomize the subject.

Urine pregnancy test in females of childbearing potential by definition are those females that have reached menarche and until becoming postmenopausal unless permanently sterile (defined as no menses for 12 months without an alternative medical cause).

Randomization may occur in IXRS the day prior to dosing for clinical logistics. Screening Visit and Randomization Visit may occur on the same day. The first dose of study treatment may occur on Day 1 or Day 2 (see Section 5.2.4)

The following activities should be done at the time of randomization.

NOTE: For therapeutic monitoring of SOC the Investigator will use discretion to decide when and how often to repeat INR or anti-FXa levels or aPTT measurements after randomization. These measurements will be taken and evaluated in the clinic, or alternatively, an optional site-specific local laboratory.

NOTE: For subjects randomized to the edoxaban arm, a blood sample will be collected before the first dose of edoxaban for PD analysis only if the subject did not receive any heparin (UFH or LMWH) or VKA 24 hours prior to randomization.

- PD blood sample for subjects randomized to edoxaban taken before dosing that day
- Discretionary anti-FXa level and/or aPTT measurement for subjects on SOC with heparin and INR assessment for the subjects on SOC with VKA
- Record any prior and/or concomitant medications used since the last visit.
- Record any AEs since screening visit, including any bleeding events.
- Urine pregnancy test (for post-menarchal females)
- Physical examination for body weight only
- Dispense study drug and record amount (number of tablets/bottles) dispensed. Prescription based, locally sourced SOC study therapy will need to be supported by a prescription identifying the type of SOC to be provided;
- Explain the study drugs and the proper daily dosing to the parent(s) or guardian(s) and subject (if applicable) using the study drug dosing calendar, and confirm that the subject understands the proper daily dosing of study drug.

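### Exclusion 7b limits ALT and bilirubin but not AST, so a child already at the 8 × ULN AST interruption level can pass every numeric liver criterion for entry

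*Combined protocol and SAP*

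**What the plan says.** **Entry.** Section 4.2, exclusion 7b, removes "Subjects with ALT >5 × the upper limit of normal (ULN) or total bilirubin (TBL) >2 × ULN with direct bilirubin >20" per cent of the total. The Protocol Synopsis carries the same rule, with the bilirubin limb worded "or total bilirubin >2 × ULN with direct bilirubin >20% of the total at Screening". AST appears in neither place. The other hepatic exclusion, 7a, is a clinical diagnosis without an enzyme value, and exclusion 15 is a general investigator-judgement clause.

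**On treatment.** Section 5.6.3 states that ALT and/or AST at or above 8 × "ULN requires an immediate interruption of study drug treatment and prompt repeat testing to confirm abnormality". The same list allows treatment to be stopped "If initiating or continuing study drug places the subject at undue hazard as determined by the Investigator".

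**Screening tests.** AST is measured. It is in the central liver panel of Section 6.2, in the liver function test definition in Section 9.8.3 and in the liver row of Table 17.1. Sites that want to speed up qualification for children living far away may decide eligibility locally. In that case "the local laboratory results (aPTT, INR, ALT, TBL, eGFR, and platelet) will be utilized and entered into the eCRF". AST is not among those six results. The sample is split and the central laboratory still analyses its share.

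**Timing.** Section 6.2 adds that "The Screening Visit and Randomization Visit may occur on the same day", and Section 6.3 allows the first dose on Day 1 or Day 2.

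**The concern.** The plan treats AST as equal to ALT once a child is on drug. The interruption rule in Section 5.6.3 names both enzymes, and so do the potential Hy's Law criteria in Sections 9.3.1 and 9.5. At entry only ALT has a limit. The two rules therefore do not join up: a child may be randomized and given a first dose at an AST value that would oblige the investigator to interrupt the drug.

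What is at stake is the safety of individual children at the first dose, and consistency between sites, since one investigator may decline such a child and another may enrol the child. The trial's estimates are not in question.

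**Working it through.** No sample size, power or error rate enters here. The check applies the written rules to possible profiles and then looks at when AST is known.

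**Inputs**
- Entry rule (4.2, 7b): exclude if ALT > 5 × ULN, or if TBL > 2 × ULN and direct bilirubin > 20% of total.
- Interruption rule (5.6.3): interrupt if ALT ≥ 8 × ULN or AST ≥ 8 × ULN.

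**Step 1: the rules side by side** (enzymes and TBL in multiples of ULN)

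| ALT | AST | TBL | Direct bilirubin | Excluded by 7b? | At interruption level? |
|---|---|---|---|---|---|
| 5 | 8 | 1 | not needed | no | yes |
| 3 | 10 | 2 | not needed | no | yes |
| 4 | 8 | 2.5 | 10% | no | yes |
| 4 | 8 | 2.5 | 30% | yes | yes |
| 6 | 1 | 2.5 | not needed | yes (ALT) | no |

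The first three rows show the gap. The fourth shows its boundary: a child who meets the bilirubin limb is excluded whatever the AST. The gap is therefore ALT ≤ 5 × ULN, AST ≥ 8 × ULN and bilirubin limb not met.

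**Step 2: margin between entry and interruption**
- ALT: 8 − 5 = 3 × ULN.
- AST: no entry limit, so no margin.
- AST with a limit of 5 × ULN: 8 − 5 = 3 × ULN, the same as ALT.

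**Step 3: is AST known before the first dose?**
- Default central route: yes. Section 6.2 makes the qualification procedures, including the liver panel, a condition of eligibility, and Section 6.3 has the randomization system contacted only once the tests confirm eligibility. The AST value is available, but no criterion says what value disqualifies.
- Optional local route: the six deciding results are aPTT and INR (7c), ALT and TBL (7b), eGFR (8) and platelets (10). AST is left out, which follows from 7b having no AST term. If Screening and Randomization are both on Day 1, the time from sample to first dose is between 1 − 1 = 0 and 2 − 1 = 1 day. The documents give no central turnaround. If it is longer than that interval (an assumption), AST is unknown at the first dose. This is the shortest case, since Section 6.2 allows up to 30 days between Screening and Randomization.

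**Step 4: direct bilirubin.** Five screening lists were checked: the central and local lists in 6.2, Table 9.2, Section 9.8.3 and Table 17.1. Serum direct bilirubin is on 0 of 5; the bilirubin in Table 9.3 is a urine test. It is needed only when TBL > 2 × ULN and ALT ≤ 5 × ULN.

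**The case against.** The best reply is that entry limits need not mirror on-treatment limits. The 8 × ULN rule sits among the adverse-event reasons, governs a drug already being given, and calls for interruption and repeat testing, not automatic permanent withdrawal. A sponsor may choose ALT alone as its entry marker. Exclusion 7a covers named liver diseases, exclusion 15 and the undue-hazard clause cover the rest, and Section 9.2 expects investigators to appraise all laboratory results. An investigator who sees AST at 8 × ULN also knows the interruption rule.

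Much of this stands. The safeguards would probably stop some of these children. But the documents give no reason for leaving AST out at entry, and none of the safeguards supplies an AST value to judge against.

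The reply also rightly limits the timing issue. A reader might infer that AST is generally unknown at dosing. The documents do not support that: it can happen only on the optional local route, with same-day screening and randomization and a slow central result. Even there, a routine-care result from the two weeks before Screening may exist. Nor is AST's absence from the local list a separate defect, because that list simply follows the numeric criteria.

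A reader might also conclude that 7b cannot be applied because direct bilirubin is on no list. That goes too far: the criterion names the test, and a site following it would order it.

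**Conclusion.** The concern holds, at minor weight. A child with ALT at or below 5 × ULN and AST at or above 8 × ULN, who does not meet the bilirubin limb, is stopped by no numeric liver criterion although the plan requires interruption at that AST level. On the central route this follows from the text without any assumption. That AST could be unknown at first dose on the local route depends on an unstated central turnaround longer than 0 to 1 day.

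Three stronger readings are not supported:
- **Prolonged exposure.** It might be inferred that such a child stays on drug until the Month 1 liver panel. The split Screening sample is still reported and must be appraised, and the interruption rule then applies.
- **Bias in the primary bleeding comparison.** Nothing in the documents links this gap to that endpoint, and no count of affected children is given or estimated.
- **5 × ULN as the only right limit.** What follows from the plan's own rule is a limit below 8 × ULN. The value 5 is a choice matched to ALT.

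**What to change.** 1. In the Synopsis and Section 4.2, change the first limb of 7b to ALT or AST above 5 × ULN. At minimum, require AST below the 8 × ULN interruption level.
2. In Section 6.2, add AST to the local eligibility results, and require the AST result before the first dose.
3. As housekeeping only, list serum direct bilirubin as a reflex test on the existing Screening sample when TBL exceeds 2 × ULN (Sections 6.2 and 9.8.3, Table 17.1).

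The cost is wording, one more enzyme on a local panel that already includes ALT, and a short wait for its result on that route. A few more children may fail screening; Section 5.6.8 allows one retest with Sponsor approval, within 30 days of the original Screening Visit. The potential Hy's Law reporting rules in Sections 9.3.1 and 9.5 need no change.

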4.3. Additional Requirements

4.3.1. Stopping Rules for Study:

An Independent Data Monitoring Committee (IDMC) may recommend termination of the study. Termination may be made for any of the following reasons:

- Concerns about significantly higher bleeding risk relative to one of the study arms,
- Concerns about drug-induced liver injury,⁹
- Any other safety concerns based on benefit/risk evaluation by the IDMC.

5. STUDY TREATMENT(S)

5.1. Assigning Subjects to Treatments and Blinding

5.1.1. Treatment Groups

All subjects will be assessed for eligibility in the study in accordance with the inclusion/exclusion criteria. Eligible subjects will be stratified and randomized as follows:

• All eligible subjects will be stratified by:

Type of underlying heart disease:

Kawasaki disease

Fontan surgery

Heart failure (HF)

Others (which can include post-surgical procedures for congenital heart disease other than Fontan surgery)

Subjects with underlying disease other than Kawasaki will be further stratified by concomitant use of low dose aspirin (1 to 5 mg/kg/day).

• Randomized in a 2:1 ratio (edoxaban:SOC, respectively) into 1 of 2 treatment arms:

Edoxaban-treatment arm: subjects will receive a selected dose of edoxaban

OR

SOC-treatment arm: subjects will receive SOC anticoagulant according to clinical site's SOC treatment, as follows (alone or in combination):

Heparin, including UFH or LMWH

Vitamin K antagonist (VKA) with potential bridging with heparin based therapy until VKA INR is in therapeutic range

After Month 3, all subjects who continue in the Extension Period and are on SOC will be offered edoxaban treatment and dosed according to their cohort age at the time of subject consent. During the extension period of the study, check the body weight prior to dosing and adjust dosage accordingly. Frequency of dosage changing is up to the Investigator's discretion.

Subjects from 1 to <18 years of age will be enrolled in the study as soon as the dosing regimen is established for each age cohort in the Phase 1 single-dose U157 study.

Additionally, subjects less than 1 year of age will be admitted to the study after review by the IDMC of safety data of 50% of subjects in the 1 to <18 years of age group who have completed the Main Treatment Period of 3 months (50 subjects in edoxaban arm and 25 subjects in SOC arm).

Subjects younger than 6 years of age will only receive edoxaban granules for oral suspension, which will give more flexibility to adjust mg/kg dose. Doses for all age groups will be selected to elicit target exposures comparable to those achieved from the adult Phase 3 study of 60 mg.

Proprietary and Confidential Page 53 Table 5.1 indicates the edoxaban doses to be given for subjects of the ages 2 to <18 years of age. Doses for all subsequent age cohorts will be by separate notification to the investigative sites outside the content of this protocol after the IDMC has approved the proposed edoxaban doses and safety data from the U157 study.

Doses for Cohorts 1, 2 and 3 have been established. Doses for the remaining subsequent age cohorts will be by separate notification to the investigative sites outside the content of this protocol after the IDMC has approved the proposed edoxaban doses and safety data from the U157 study.

Study treatment should be administered on the same day as randomization (Day 1) if INR is \leq 2.5 for subjects receiving VKA prior to randomization.

5.1.1.1. Edoxaban-Treatment Arm (Randomization through Month 12, and All SOC Subjects Converted to Edoxaban after Month 3)

Edoxaban treatment will be packaged and dispensed to the subject on a monthly visit schedule. For subjects who cannot pick up their study therapy on a monthly basis, accommodations will be made to allow the Investigator to distribute up to a 3-month supply of study drug to match the scheduled study visit interval. Edoxaban will be given orally at the appropriate dose depending on the results of the ongoing U157 study.

Cohort 1 (12 to <18 years old) and Cohort 2 (6 to <12 years old) will receive tablets (15 and/or 30 mg strength, see Table 5.1) or offered granules for oral suspension if swallowing is an issue. Subjects <2 years of age will take edoxaban granules for oral suspension which will provide more flexibility to adjust mg/kg dose. Subjects will be instructed to take the edoxaban dose orally once a day, at the same time every day, preferably in the morning, with or without food. Tablets should be swallowed with a glass of water. One bottle of edoxaban granules should be used for each dosing day. The recommended dosing for the 12 to <18, 6 to <12, and 2 to <6 year olds is shown in Table 5.1.

Dosing recommendations for the lower age cohorts will be provided as the U157 single-dose edoxaban study completes the PK exposure analysis for similar age cohorts. Doses for all subsequent age cohorts will be by separate notification to the investigative sites outside the content of this protocol.

